The first step in data analysis is to determine models for longitudinal data collected. These models are usually based on our knowledge of how these data behave and details of the study. These models can also be checked to see whether they fit the data by viewing data for each patient without regard to patient group. For instance, BMD can be assumed to increase linearly over the study duration. We hypothesize that this linear increase will be slowest in untreated AA patients and intermediate in those on oral estrogen, and the smallest effect size would be the difference between groups randomized to transdermal versus oral estrogen. We would check this linearity by looking at data from individual patients and checking that actual measurements are normally distributed around the patient's linear trajectory by looking at residuals (difference between observed value and trend line). It is possible that in some cases linearity and normality might hold after a log or other transformation. If linearity holds for actual or transformed values, variables will be analyzed by mixed model ANOVA, a common method for analyzing longitudinal data. One advantage of this method is that it allows us to use data from subjects that drop out early. The linear model is appropriate for BMD, but will not be appropriate for variables that may be relatively constant during treatment. These might include measurements of bone turnover and hormones. These would be modeled assuming that each patient has a constant level. After examining how well the assumed model fits the data, repeated measures ANOVA will be used for analysis. In this model there is a fixed treatment term of primary interest. Measurements at each time are assumed to be a multivariate observation with an unspecified variance covariance matrix.

Power calculation for primary endpoint: Power analysis is based on the primary endpoint, i.e. average change in BMD over one year in a randomized trial comparing mean change in spine BMD in young women 14-25 years old with AA randomized to transdermal estrogen versus oral estrogen or no therapy for one year. Girls with AA will be stratified based on spine BMD Z-scores (≤ -1 or > -1).

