Our preliminary data indicate a relative increase in spine BMD of 4.7% over one year with transdermal estrogen vs. no therapy. In addition, one study in AA women has reported a 1.5% relative increase in BMD in AA women following oral estrogen vs. placebo. Our preliminary data indicate that the SD for change in lumbar BMD over a year is 2.7%. Based on these data, using the Dunnett's test, a total of 99 AA (33 each in the two treatment arms no-treatment arm) will be needed to detect a difference of 3.2% (4.7%-1.5%) in mean %increase in spine BMD in groups receiving transdermal vs. oral estrogen, with a power of 80%, using a two sided $p=0.05$ level test.

The estimated sample size of 99 subjects with AA does not take into account study drop-outs. Based on previous studies, we expect an 8- 10% drop-out rate over one year. We thus estimate that we will need to recruit 109 subjects with AA (37 in the transdermal estrogen arm, and 36 each in the oral estrogen and no-treatment arms) to have 99 evaluable subjects at the end of the study. An independent Data and Safety Monitoring Board (consisting of an adolescent medicine physician, a statistician, a bone

expert, a pediatric endocrinologist and a psychiatrist) will review data regarding adverse events, study deviations and violations at study initiation and every six months. BMD information will be presented to the DSMB at each meeting, and study termination considered for subjects demonstrating >10% decrease in spine BMD from baseline, if randomized to estrogen.

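### The sample-size statement does not follow from its own inputs: 80% power for a 3.2% difference with SD 2.7% under Dunnett's test needs about 15 per arm, and the stated 33 per arm gives 99.4% power

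*SAP*

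**What the plan says.** The SAP section on the power calculation for the primary endpoint (one-year change in spine BMD in amenorrheic athletes, AA) gives all its inputs together.

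- **Effect.** Preliminary data show a "relative increase in spine BMD of 4.7% over one year with transdermal estrogen vs. no therapy", and one published study is said to show 1.5% for oral estrogen against placebo. The target is the difference between these, 4.7% − 1.5% = 3.2%.
- **Spread.** "Our preliminary data indicate that the SD for change in lumbar BMD over a year is 2.7" per cent.
- **Test and error rates.** Dunnett's test, two-sided 5% level, 80% power.
- **Result.** "a total of 99 AA (33 each in the two treatment arms no-treatment arm) will be needed to detect a difference of 3.2" per cent, for transdermal against oral.
- **Drop-out.** With 8–10% loss, 99 becomes 109 recruited (37 + 36 + 36).

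The SAP's preceding text on longitudinal models says that "the smallest effect size would be the difference between groups randomized to transdermal versus oral estrogen", so this is the contrast meant to drive the sample size.

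**The concern.** A difference of 3.2% against an SD of 2.7% is a standardised effect of 3.2/2.7 = 1.19, which is large. Effects of that size need roughly a dozen or so subjects per arm for 80% power, even with a multiplicity adjustment, so 33 per arm is out of line.

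Two things are at stake. If the inputs are right, the 80% figure and the claim that 99 are needed are both false, and the trial is powered for a much smaller effect than it states. If 33 per arm was correctly derived, some input behind it is not the one printed. In that case the apparent surplus of power may not exist, for example if the SD used was nearer 4.2%. The reading of a null result for transdermal against oral depends on which is true. This is also the only sample-size justification for a trial that randomises participants as young as 14 to hormone treatment or none.

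The text also disagrees with its own numbers on the smallest effect. The SAP assigns that role to transdermal versus oral (3.2%), yet its figures make oral versus no therapy (1.5%) smaller. This does not explain 33 per arm, but it suggests that reasoning and figures were not reconciled.

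**Working it through.** **Inputs, all from the SAP's power section.** Difference δ = 3.2%; SD σ = 2.7%; three equal arms; Dunnett's test; two-sided α = 0.05; power 80%. I take transdermal as the common reference arm, because the endpoint is described as transdermal versus oral or no therapy. The SAP does not name the reference.

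**Formulae.** For n per arm:

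- standard error of a difference = σ·√(2/n)
- noncentrality λ = δ / [σ·√(2/n)]
- pooled degrees of freedom = 3(n − 1)
- c = two-sided Dunnett critical value for two comparisons with correlation 0.5
- power = P(T > c), where T is noncentral t with those degrees of freedom and noncentrality λ (the opposite tail is negligible)

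**Trying to reproduce 33 per arm at 80% power.**

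| n per arm | df | c | σ·√(2/n) | λ | Power |
|---|---|---|---|---|---|
| 14 | 39 | 2.295 | 1.021 | 3.136 | 79.6% |
| 15 | 42 | 2.289 | 0.986 | 3.246 | 82.7% |
| 33 | 96 | 2.245 | 0.665 | 4.814 | 99.4% |

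The stated figure is not reproduced. The requirement is 15 per arm, 3 × 15 = 45 in total, against 99; 33/15 = 2.2. Simulation with 200,000 runs agrees: 82.7% at 15 per arm and 99.5% at 33 per arm (0.9946, against an exact value of 0.9945).

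**What 33 per arm does correspond to.** 80% power at 33 per arm needs λ ≈ 3.09.

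- With σ = 2.7%: δ = 3.09 × 0.665 ≈ 2.06%.
- With δ = 3.2%: σ = 3.2 / (3.09 × √(2/33)) ≈ 4.20%. With an unadjusted t-test the SD would have to be 4.57%.

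**Other readings tried (n per arm; δ = 3.2%, σ = 2.7% and 80% power unless noted).**

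| Reading | n per arm |
|---|---|
| Unadjusted two-sided t-test | 13 (79.2% at 12, 82.6% at 13) |
| One-sided, unadjusted (normal approximation) | 9 |
| Bonferroni, 2 or 3 comparisons (normal approximation) | 14 or 15 |
| Dunnett, power 90%, 95%, 99% | 19, 23, 31 |
| Dunnett, α = 0.01, power 80% or 90% | 21 or 25 |
| SD × √2 (= 3.82%), power 80% or 90% | 28 or 36 |
| Full power within each of the two Z-score strata | 30 |
| Transdermal vs none, δ = 4.7% | 8 |
| Oral vs none, δ = 1.5% | 62 |

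None gives 33. At 33 per arm, power is near 100% for 4.7% and 50.7% for 1.5% at the same critical value. The last figure serves only to show that this contrast does not explain 33 either; the trial was not sized for it. Requiring both Dunnett comparisons to succeed does not help, since joint power at 33 per arm is still 99.5% by simulation.

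**Drop-out step.** 99/(1 − d) rounds up to 108, 109 and 110 for d = 8%, 9% and 10%. The move from 99 to 109 is consistent, so the fault lies in the core calculation.

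**The case against.** The best defence is that the error is harmless in direction. On the stated inputs the transdermal–oral contrast has more power than claimed; no test becomes invalid, no estimate is biased and the type I error is unchanged. That is correct, and it is why enrolment need not change. It does not make the statement right, and the surplus is real only if the printed SD and difference are the true planning values.

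A second point is that 33 may contain an unstated allowance rather than a wrong input. Randomisation is stratified by spine Z-score, and full power in each stratum would need 30 per arm. Reading 2.7% as the SD of a single measurement would need 28, and 33 per arm would then have 87.5% power. Neither gives 33 and the SAP states neither, but an undisclosed allowance cannot be excluded.

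Third, transdermal as the Dunnett reference is an inference. It is the natural reading, and the result barely depends on it: the unadjusted test needs 13 per arm.

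Finally, the Protocol gives 145 AA where the SAP recruits 109. That is a separate discrepancy and does not explain 33 evaluable per arm.

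**Conclusion.** The concern holds. The stated difference, SD, test, level and power require 15 evaluable per arm (45), not 33 (99), an excess of 2.2 times. At 33 per arm the power for 3.2% is 99.4% rather than 80%, and the difference detectable with 80% power is 2.06% rather than 3.2%. Either a printed figure is wrong or an input or allowance is missing; the documents do not show which.

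The calculation assumes equal arms, a common SD, pooled variance and transdermal as the reference. The gap is far too wide to be rounding or a choice of approximation. The 3.2% is itself the difference of two effects from separate sources, so it is a planning assumption; that does not affect the arithmetic.

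**What to change.** Leave the evaluable target at 33 per arm and correct the SAP text in one of two ways.

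1. If SD 2.7% and difference 3.2% were the planning values, state that with 33 evaluable per arm and a Dunnett-adjusted two-sided 5% test with transdermal as the reference arm (sponsor to confirm), power is above 99% for 3.2%, and 80% power is reached at a difference of about 2.1%.
2. If another SD, target difference, power or design allowance was used, state it with its source and re-run the calculation.

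In either case, amend the sentence on the smallest effect so that it agrees with the 3.2% and 1.5% figures. The cost is SAP wording and one recalculation, with no added patients or procedures.

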Subjects will be 14-25 year old female athletes with AA (n= 145), EA (n=), and female non-athletic controls (n= 42). Because different kinds of physical activity have different effects on bone metabolism, we will enroll only endurance athletes (please see Inclusion Criteria).

For Specific Aims 7-8, 40 adolescent and young adult male athletes 14-21 years old, and 20 adolescent and young adult male non-athletes 14-21 years old will be studied. Eligibility will be assessed over the phone, and the study will include one visit only.

Participation of Children: We will enroll only female adolescents/young adults to optimize power and avoid issues arising from deficiencies of different predominant sex hormones in boys (testosterone) vs. girls (estrogen). Adolescents and young adults will be studied to determine effects on BMD and its predictors in a population that should be actively accruing bone.

Inclusion Criteria

(i) Females 14-25 years old: Our pilot data are reassuring in that young women 14-25 years old with hypothalamic amenorrhea are not adversely affected with estrogen use. In fact, in our prospective study, beneficial effects were observed both in young women 18-25 years old using oral estrogen, and in 14-18 year old adolescent girls using transdermal estrogen. We therefore feel that including girls in the 14-21 year age range will not be hazardous to their bone health. In fact, given the lack of data in this age group, it is important to study younger women and teenagers rather than extrapolate data from studies in adults to this younger population. Hormone dynamics differ in teenagers compared with adults, and bone mass accrual is even more dependent on estrogen and IGF-1 in younger than older women who have already achieved peak bone mass.

(ii) Bone age (BA) \geq 14 years: 98% of adult height is achieved at a BA of 14 because only 2% of growth potential persists at a BA of 14 years. Thus, to avoid potential stunting of growth potential with estrogen replacement, we have chosen to include girls with BA of \geq 14 years.

(iii) BMI between 10th-90th percentiles for age, or BMI of at least 85% of ideal BMI

(iv) Amenorrhea (for AA): absence of menses for \geq three months (74) within a period of oligomenorrhea (cycle length $>$ six weeks) for \geq six months, or absence of menarche at ≥ 16 years

(v) Eumenorrhea (EA and controls): \geq nine menses (cycle length 21-35 days) in preceding year.

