- (iii) Endurance athletes engaged in sports that involve weight bearing training of the legs. Severity of low BMD and gonadal dys-function may differ by type of exercise (131). By limiting enrollment to weight bearing endurance athletes, we will eliminate variability from type of activity. Endurance training is defined as \geq 4h of aerobic weight-bearing training of the legs or specific endurance training weekly, or \geq 20 miles of running weekly for \geq 6 months in the last year. Cyclists, rowers and swimmers will not be included because these activities do not involve lower extremity weight bearing. Gymnasts will not be included (not an endurance sport),
- (iv) Non-athletes will be eligible if weight bearing exercise activity is $<$ 2h a week and they are not participating in organized team sports.

Exclusion Criteria:

- (i) Use of medications affecting bone metabolism (washout period of 3 months prior to enrollment if medically permissible to discontinue these)
- (ii) Conditions other than endurance training that may cause hypogonadism or low bone density
- (iii) High TSH, FSH or prolactin
- (iv) Standard MRI exclusion criteria such as presence of pacemaker, intracranial metal clips, severe claustrophobia

Briefly describe study procedures. Include any local site restrictions, for example, "Subjects enrolled at Partners will not participate in the pharmacokinetic portion of the study." Describe study endpoints.

Over the proposed 5-year investigation, 145 teenage girls and young adults 14-25 years old with AA, 42 EA and 42 non-athletic controls will be studied. Eligibility will be assessed at the screen, and the study will include a baseline visit and follow up visits at 3, 6, 9 and 12 months. The baseline visit will occur within 8 weeks of the screen. EA and controls will be followed without intervention (except elemental calcium and vitamin D) for 12 months.

For Specific Aim 3 we anticipate screening 2 times the number of athletes that we will eventually enroll in the study to obtain 145 eligible AA adolescents. In addition, for Specific Aims 1 and 2, we anticipate screening 2 times the number of EA (n=42) and non-athletic controls (n=42) required for this section of the study (total subjects to be screened= 458).

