- (g) Indirect calorimetry and handgrip strength. This exam will be performed at the Clinical Research Center at Massachusetts General Hospital or at the Charlestown Navy Yard site. This exam will be completed sometime in between screening and baseline visits or at the baseline visit.
- (h) Bone microarchitecture at the ultradistal radius and leg (non-dominant) will be assessed using X-treme CT in a subset of 100 AA (first ~33 in each randomization group), 36 EA, 36 controls sometime between the screening and baseline visits or at the baseline visit
- (i) MRI (regional fat and muscle) assessment
- (j) Finite element analysis (FEA) will also be performed.
- (k) Optional fMRI and evaluation through the State Trait Anxiety Inventory (STAI) scores and addictive behaviors using the Alcohol Use Disorder Identification Test (AUDIT) and Drug Abuse Screening Test-10 (DAST-10) in subset of 6 AAs randomized to treatment, 6 EAs, and 6 HC 18-25 years.

Follow-up Outpatient Study Visits at 6 and 12 months: These will include:

- (a) History and physical examination with anthropometric measurements, adverse event review, changes to health status (including mood disorders)
- (b) Bouchard 3-day activity record (daily energy expenditure), 4-day food diary (caloric intake), EDI-2, TFEQ, REE (indirect calorimetry)
- (c) Handgrip strength in 60 AA (20 in each treatment group) (after drop-outs), 20 EA, controls
- (d) BMD and body composition using DXA (lumbar spine, hip, total body)
- (l) 12 m only: Bone structure at the ultradistal radius and leg (X-treme CT) in the 90 AA, 30 EA and 30 controls (after dropouts); MRI (regional fat and muscle) assessment. Finite element analysis (FEA) will also be performed.
- (e) Salivary cortisol at 11 p.m.
- (f) Fasting (or 2 hour post-prandial) blood samples for leptin, adiponectin, ghrelin, PYY, IGF-1, insulin, estradiol, testosterone, SHBG, FSH and LH, bone turnover markers (PINP and N-telopeptide).
- (g) Color-Word Interference Test subtest from DKEFS and the CVLT.
- (h) Follow up of fMRI and evaluation through the State Trait Anxiety Inventory (STAI) scores and addictive behaviors using the Alcohol Use Disorder Identification Test (AUDIT) and Drug Abuse Screening Test-10 (DAST-10) at 6 month visit only in the 6AAs scanned at baseline.

Follow-up Outpatient Study Visits at 3 and 9 months (abbreviated safety evaluation visits):

- (a) History and physical examination with anthropometric measurements, adverse event review

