FEA is an established analytical engineering technique to estimate stresses and strains induced by mechanical loading of complex structures, and is used to study bone strength in humans. Micro-finite element techniques applied to data from HR-pQCT strongly predict *in vitro* femoral and vertebral breaking strength independent of DXA-derived BMD (179, 180). Spine FEA differentiates patients with and without vertebral fractures (181) and hip FEA predicts new hip fractures independent of DXA-derived BMD (182). HR-pQCT is used for FEA using micro-finite element (μ FE) techniques (183-185). In this context, FEA parameters correlate more strongly with failure load of the distal radius than either bone mass or microstructure (161) and clarify the structural mechanisms underlying fragility in subjects with fractures (159), including those occurring during the adolescent growth spurt (160). Of note, FEA estimates of bone strength have not been reported in female athletes, nor has FEA been utilized to monitor response to therapeutic intervention in this population. FEA will be assessed in 66 AA, 22 EA and 22 controls at baseline and 60 AA, 20 EA and 20 controls (after anticipated drop-outs) at 12m.

fMRI and Evaluation of Cognition, Mood, and Addictive Behaviors:

Exercise can impact neural functions on many fronts, including decreasing anxiety and addictive behavior, and improving cognition. We would like to assess a subset of 6 AAs, 6 EAs, and 6 HCs ages 18-25 years. This will be an optional portion of the study, with a separate section of the consent form to address this. fMRI scanning will be performed using (i) the stop-signal task for assessing cognition and (ii) estroop task for assessing anxiety. The EAs and AAs will receive one fMRI scan at baseline. The AAs will receive one scan at baseline and a follow-up scan at the 6 month visit.

Stop signal task: In this task, participants will categorize visual stimuli as fast as possible but are instructed to withhold a response when a stop signal appears on a randomly selected 25% of all trials. The time delay between the onset of the imperative stimulus and the stop signal will be adapted to the participants' individual response times using a staircase tracking algorithm. A mathematical framework allows for estimating the duration of the stop process ("stop signal reaction time") based on the distribution in the go trials as measure of duration of the inhibition process and therefore inhibition ability

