Subjects will be recruited over a four year period, thus at the rate of about ~ 40 subjects per year (27 AA, 12 EA and healthy adolescents). The accrual goal is reasonable given systems of referral already in place from our studies in girls with anorexia nervosa. We have collaborations ongoing with primary care providers, psychiatrists, therapists, dieticians and adolescent medicine physicians in the New England area for patients with eating disorders and the female athlete triad. Our group informs these providers about new studies, and providers then present studies to their patients who contact our group if interested in study participation. We have been very successful in our recruitment efforts in girls with anorexia nervosa, and expect recruitment of AA to be easier given that prevalence of female athletes is higher than that of anorexia nervosa, and because AA girls have fewer psychiatric co-morbidities compared with girls with anorexia nervosa. In addition, a co-investigator in this grant is [name], who is a very well known for his work with athletes. [name] was until recently a Professor in the Department of Health Sciences at the Sargent College of Health & Rehabilitation Sciences, Boston University, a member and Fellow of the American College of Sports Medicine and a Certified ACSM program Director. Given [name] expertise in this field and access to providers looking after athletes, we anticipate recruitment to be steady and to be completed in the specified period. Mailings will also be sent out to our regional high schools. In addition to mailing lists already in place, we are preparing mailing lists of area Sports Medicine specialists who are most likely to see young athletes. We anticipate completing enrollment in four years; such that the last subject will complete the one-year follow up by the end of the fifth year. We anticipate another month will be required by the Core Laboratory to run samples for secondary endpoints, and two months for data analysis. Three months will be necessary to write up results of the study. Study duration is thus anticipated to be 5.5 years.

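### The protocol enrols 145 amenorrheic athletes and the SAP of the same date 109 for the same three-arm comparison; nothing reconciles them, and the protocol's own recruitment rate fits 109

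*SAP*

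**What the plan says.** **SAP, power calculation for the primary endpoint.** The SAP asks for 99 evaluable AA, 33 in each of the transdermal, oral and no-treatment arms. It allows 8-10% drop-out over the year and concludes: "We thus estimate that we will need to recruit 109 subjects with AA", divided 37/36/36.

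**Protocol, Research Design and Methods.** The design paragraph reads "Subjects will be 14-25 year old female athletes with AA (n= 145), EA (n=), and female non-athletic controls (n= 42". The study-procedures text repeats the AA number: "145 teenage girls and young adults 14-25 years old with AA, 42 EA and 42 non-athletic controls will be studied". It then ties that number to Specific Aim 3, which is the randomised trial: "For Specific Aim 3 we anticipate screening 2 times the number of athletes that we will eventually enroll in the study to obtain 145". The screening total given there is 458.

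**Protocol, subset sizes.** X-treme CT at baseline is planned in "a subset of 100 AA (first ~33 in each randomization group", and at 12 months "in the 90 AA, 30 EA and 30 controls (after dropouts". For finite element analysis, "FEA will be assessed in 66 AA, 22 EA and 22 controls at baseline and 60 AA" at 12 months.

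**Protocol, Recruitment Procedures.** Recruitment runs for four years, "at the rate of about ~ 40 subjects per year (27 AA, 12 EA and healthy adolescents". The last 12-month follow-up is to be finished within five years.

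Both documents are dated December 4, 2014. Neither refers to the other's AA number.

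**The concern.** Two documents of the same date give different numbers to randomise in the same comparison. The 145 is not an isolated misprint, because it appears three times in the protocol and the screening total depends on it. The 109 is not isolated either, because it follows from the SAP's evaluable number and agrees with the protocol's own AA recruitment rate. The protocol therefore disagrees with itself as well as with the SAP.

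At stake is what counts as the planned trial. The intended randomised number, arm sizes and evaluable number for the primary comparison cannot be settled by reading both documents. If enrolment closed at 109, one reader would see a completed trial and another a trial 36 short, and the decision to stop enrolling would be open to question. If 145 is meant, the stated timeline does not hold.

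**Working it through.** **1. The SAP's 109 reproduces.** Inputs: 99 evaluable, drop-out 8-10% (SAP). Recruited = evaluable / (1 - drop-out).
- 99/0.92 = 107.6 and 99/0.90 = 110.0, a range that contains 109.
- 37 + 36 + 36 = 109, and the implied drop-out is 1 - 99/109 = 9.2%.

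**2. The protocol's 458 reproduces from 145.** The rule is to screen twice the number enrolled.
- 2 x (145 + 42 + 42) = 2 x 229 = 458.
- With 109 it would be 2 x (109 + 42 + 42) = 2 x 193 = 386.

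**3. Drop-out does not connect the two numbers.**
- The protocol's own AA allowances are 1 - 90/100 = 10.0% (X-treme CT) and 1 - 60/66 = 9.1% (finite element analysis), in line with the SAP.
- 145 x 0.90 = 130.5 and 145 x 0.92 = 133.4 evaluable, not 99.
- To end at 99 from 145, drop-out would have to be 1 - 99/145 = 31.7%.

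**4. Size of the gap.** 145 - 109 = 36, and 36/109 = 33%. The protocol gives no arm sizes for 145. Assuming equal allocation, 145/3 = 48.3, so 48-49 per arm instead of 36-37. Evaluable per arm would be 130.5/3 = 43.5 to 133.4/3 = 44.5, instead of 33.

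**5. Accrual (protocol rate of 27 AA a year for four years).**

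| | 109 AA | 145 AA |
|---|---|---|
| Recruited in four years at 27 a year | 108 | 108 (37 short) |
| Years needed at 27 a year | 109/27 = 4.0 | 145/27 = 5.4 |
| Last 12-month visit (years from start) | 5.0 | 6.4 |
| Rate needed for four years | 109/4 = 27.25 | 145/4 = 36.25 |

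**6. Eumenorrheic athletes (EA) and controls.** The requirement is 42 + 42 = 84. The stated 12 a year can be read in two ways.
- Combined: 12 x 4 = 48, below 84. The yearly total is 27 + 12 = 39, which matches the stated figure of about 40.
- Per group: 24 x 4 = 96, enough for 84. The yearly total is then 27 + 24 = 51, which does not match.

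**7. Power on the SAP's inputs.** Difference 3.2, SD 2.7, two-sided 0.05, Dunnett. The SAP does not name the reference arm; I assume two comparisons sharing the transdermal arm (correlation 0.5). Degrees of freedom are 3n - 3, the noncentrality is (3.2/2.7) x sqrt(n/2), and power comes from the noncentral t distribution.

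| n per arm | Critical value | Power |
|---|---|---|
| 14 | 2.295 | 0.796 |
| 15 | 2.289 | 0.827 |
| 33 | 2.245 | 0.994 |
| 43 | 2.237 | 0.9994 |
| 44 | 2.237 | 0.9995 |

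Power first exceeds 80% at 15 per arm. The stated 80% therefore does not explain 33 per arm, and it cannot explain 109 or 145.

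**The case against.** The strongest reply is that the SAP gives a minimum and the protocol an enrolment plan. Enrolling 145 satisfies a requirement of 109, and AA also serve the cross-sectional and observational aims. Over-enrolment of that kind can be legitimate. But neither document says that 145 is deliberate over-enrolment, and the protocol assigns the number to the randomised aim. A derivation may exist in the grant that the SAP mentions; it would still leave the arm sizes and the accrual plan unreconciled.

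Two features of the protocol might account for extra AA. The exclusion criteria have a separate list for AA to be randomised, which could imply that some AA are studied without randomisation. The screening-visit text gives AA dancers their own randomisation template, which the SAP does not mention. Neither comes with a count, and neither is offered as the source of the 36. They do mean that the per-arm figures under 145 are inferred.

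The recruitment sentence is also loose evidence. About 40 a year for four years is 160, which matches neither 229 (with 145 AA) nor 193 (with 109 AA). This limits what the sentence can show about which target was intended. It does not remove the conflict between 27 AA a year for four years and 145 AA.

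Finally, the SAP's sample-size paragraph is coherent from 99 to 109 and power is ample at either target. Both points stand, and they limit the seriousness of the problem.

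**Conclusion.** The concern holds, and the plan is wrong as written. Two AA targets, 109 and 145, are given for one randomised comparison, and neither drop-out nor any statement in the documents links them. The AA recruitment rate and the five-year timeline support 109; the screening total supports 145. The documents do not show which was intended.

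This should be fixed, but it does not threaten the primary comparison: on the SAP's difference and SD, power for transdermal versus oral estrogen is about 0.994 at 33 per arm and above 0.999 at 43-44. The test and the estimand do not change. The harm is an unexplained target and, if 145 is meant, a timeline that overruns by about 1.4 years (6.4 against 5).

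The gap of 36, the drop-out figures and the accrual figures are arithmetic on stated numbers. The per-arm figures under 145 assume that all 145 are randomised equally. The 6.4 years assumes a constant 27 AA a year. The power figures assume the Dunnett structure set out above.

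**What to change.** State one AA target in both documents, with its arm sizes, drop-out allowance, evaluable number and recomputed power.

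- **If 145 is intended:** revise the SAP (48-49 per arm and about 130-133 evaluable under equal allocation) and say why the target exceeds the powered number. If some AA are not to be randomised, or dancers are an added group, give their numbers. Then either justify about 36 AA a year or lengthen the four-year enrolment period and the dates that follow from it.
- **If 109 is intended:** correct the three statements of 145 in Research Design and Methods and change the screening total to 386.
- **In either case:** say whether 12 a year covers EA and controls together or each group separately, and make that rate yield 84. Restate the power for the chosen number, since the SAP's inputs reach 80% at 15 evaluable per arm, not 33. If 33 rests on a smaller difference or a larger SD, give those inputs.

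The cost is text changes in both documents, with no added procedures. Keeping 145 also carries the cost of faster or longer recruitment.
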